2.2 Secondary Goals

2.21 To evaluate safety of pembrolizumab in this patient population.

2.22 To evaluate response rates of pembrolizumab in this patient population.

2.23 To determine the progression free survival, duration of response, time to response and overall survival of pembrolizumab in this patient population .

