13.7 Ineligible

A patient is deemed *ineligible* if after registration, it is determined that at the time of registration, the patient did not satisfy each and every eligibility criteria for study entry. If the patient received treatment, the patient may continue treatment at the discretion of the physician as long as there are not safety concerns. The patient will continue in the Active Monitoring/Treatment phase of the study, as per section 4.0 of the protocol.

- If the patient never received treatment, on-study material must be submitted. Survival Follow-up will be required per Section 4.0 of the protocol.

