16.4 Analysis Plan

16.41 Primary Outcome Analysis: The mSWAT score at baseline and cycle 9 will be used for change in baseline calculations. All calculated values will use the last-observation-carried forward for any participants who withdraw, are lost to follow up, or exit the study per protocol. The proportion of successes will be estimated by the number of successes divided by the total number of evaluable patients will be analysed using Mann-Whitney U for nonparametric data and the student t-test. Confidence intervals for the true success proportion will be calculated according to the approach of Duffy and Santner (Duffy D 1987).

16.42 Secondary Outcome Analysis: These analyses will include all patients meeting the eligibility criteria who have signed a consent form and have begun treatment, including patients who fail to achieve a complete or partial response.

Adverse Events: All eligible patients that have initiated treatment will be considered evaluable for assessing adverse event rate(s). The maximum grade for each type of adverse event will be recorded for each patient, and frequency tables will be reviewed to determine patterns. Additionally, the relationship of the adverse event(s) to the study treatment will be taken into consideration.

Response Rates:

Changes in mSWAT scores from baseline will be evaluated at cycle 9. Summary statistics will be calculated.

Patients will be assigned response based on the mSWAT criteria in section 11.0. Proportions of patients will be calculated and described using summary statistics. Proportions of interest are patients having CR, CR90 and PR; patients having stable subcutaneous disease; patients having progressive cutaneous disease; and patients having an overall systemic response rate.

Progression free survival time is defined for all evaluable patients as the time from registration to relapse or death due to any cause. Patients are censored if they have not achieved a progression at the time of analysis. The distribution of progression-free survival will be estimated using the method of Kaplan-Meier. In addition, the progression-free survival rate at 5 years after registration will be reported.

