16.6 Data Safety and Monitoring

- 16.61 The study statistician will review the study weekly to monitor accrual, endpoints and adverse events. Additionally, the Mayo Clinic Cancer Center (MCCC) Data Safety Monitoring Board (DSMB) is responsible for reviewing accrual and safety data for this trial at least twice a year, based on reports provided by the MCCC Statistical Office.
- 16.62 This study will be monitored by the Clinical Data Update System (CDUS) version 2.0. A full report containing cumulative CDUS data will be submitted quarterly to CTEP by electronic means. Reporting time points are: January 31, April 30, July 31, and October 31.
- 16.63 Adverse Event Stopping Rules: The stopping rules specified below are based on the knowledge available at study development. We note that the Adverse Event Stopping Rule may be adjusted in the event of either (1) the study re-opening to accrual or (2) at any time during the conduct of the trial and in consideration of newly acquired information regarding the adverse event profile of the treatment(s) under investigation. The study team may choose to suspend accrual

because of unexpected adverse event profiles that have not crossed the specified rule below.

Accrual will be temporarily suspended to this study if at any time we observe events considered at least possibly related to study treatment (i.e. an adverse event with attribute specified as “possible,” “probable,” or “definite”) that satisfy one of the following:

- if 2 or more patients in the first 10 treated patients (20%) experience a grade 4 or higher non-hematologic adverse event at least possibly related to treatment.
- if after the first 10 patients have been treated, 20% of all patients experience a grade 4 or higher non-hematologic adverse event at least possibly related to treatment.

We note that we will review grade 4 and 5 adverse events deemed “unrelated” or “unlikely to be related”, to verify their attribution and to monitor the emergence of a previously unrecognized treatment-related adverse event.

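### The adverse-event tables in section 16.42 are limited to eligible treated patients, so they would omit a dosed patient later found ineligible who may remain on pembrolizumab

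*Combined protocol and SAP*

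**What the plan says.** Section 16.42 sets the population for the secondary analyses in its opening sentence: "These analyses will include all patients meeting the eligibility criteria who have signed a consent form and have begun treatment". The paragraph on adverse events repeats the condition: "All eligible patients that have initiated treatment will be considered evaluable for assessing adverse event rate(s". The output is the maximum grade of each event type per patient, reviewed in frequency tables.

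Section 13.7 classes a patient as ineligible when, after registration, "it is determined that at the time of registration, the patient did not satisfy each and every eligibility criteria for study entry". One missed criterion is enough, and no time limit is given. For patients already dosed it says: "If the patient received treatment, the patient may continue treatment at the discretion of the physician as long as there are not safety concerns". It adds: "The patient will continue in the Active Monitoring/Treatment phase of the study, as per section 4.0 of the protocol". The test schedule in section 4.1 has an adverse-event assessment at every visit of that phase.

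The adverse-event stopping rule in section 16.63 has a different base. Its first limb applies "if 2 or more patients in the first 10 treated patients (20%) experience a grade 4 or higher" non-hematologic event at least possibly related to treatment, with no eligibility condition.

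Safety is the first of the secondary goals in section 2.2: "To evaluate safety of pembrolizumab in this patient population". The document defines no separate all-treated safety set.

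**The concern.** Drug risk follows exposure. The plan foresees patients who are exposed, may stay on treatment and are monitored, and then leaves them out of its planned safety summary for a reason that has nothing to do with exposure. Because section 13.7 has no cut-off, eligibility could also be re-judged after an event is known, so the denominator is not fixed before the outcome.

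At stake is whether the adverse-event rates describe everyone who received pembrolizumab, and whether they can be reconciled with the count used for the stopping rule. In a group of 10, one patient is a large share of the data.

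**Working it through.** **1. Where a dosed, later-ineligible patient is counted**

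| Place in the document | Counted? |
|---|---|
| Section 13.7 with schedule 4.1 (adverse-event assessment) | Yes, stays in Active Monitoring |
| Section 10 (expedited and routine reporting) | Yes, no eligibility condition |
| Section 16.63 (adverse-event stopping rule) | Yes, treated patients |
| Section 16.42 (rates and frequency tables) | No, eligible and treated |

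The omission is confined to the last row, which is the planned safety summary.

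**2. The plan's own figures**

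- Section 16.63: 2/10 = 20%, as stated.
- Section 16.31: 28 × 1.10 = 30.8, rounded up to the stated maximum of 31, an allowance of 3 patients. The allowance pools ineligibility with cancellation, major violation and other reasons, so no ineligibility rate can be taken from it.
- Accrual after Amendment 4: 10 patients.

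**3. Effect on a rate**

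Let N be the treated patients, k the dosed ineligible patients, x the patients with the event, and y those of the x who are excluded. The all-treated rate is x/N. The 16.42 rate is (x − y)/(N − k). N = 10; k, x and y are assumed for illustration.

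| k | x | y | All treated | Under 16.42 |
|---|---|---|---|---|
| 1 | 2 | 1 | 2/10 = 20.0% | 1/9 = 11.1% |
| 1 | 2 | 0 | 2/10 = 20.0% | 2/9 = 22.2% |
| 1 | 1 | 1 | 1/10 = 10.0% (exact 95% CI 0.3% to 44.5%) | 0/9 = 0% (0% to 33.6%) |
| 1 | 1 | 0 | 1/10 = 10.0% | 1/9 = 11.1% |
| 2 | 2 | 1 | 2/10 = 20.0% | 1/8 = 12.5% |

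In the first row the treated-patient count meets the 16.63 threshold (if both events are of the type that the rule names), while the 16.42 table shows 11.1%. In the third row the event disappears from the rate table.

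**4. Direction**

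The 16.42 rate is lower than the all-treated rate only when y/k > x/N, that is, when the excluded patients have the higher event rate. With k = 1:

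- Excluded patient had the event: the rate falls by x/10 − (x − 1)/9 = (10 − x)/90, which is 10.0 points at x = 1 and 8.9 points at x = 2.
- Excluded patient did not: the rate rises by x/9 − x/10 = x/90, which is 1.1 points at x = 1 and 2.2 points at x = 2.

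If ineligibility is unrelated to events, these balance on average. At x = 2: 0.2 × 1/9 + 0.8 × 2/9 = 0.20. A systematic bias therefore needs a link between ineligibility and events.

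**5. How likely is any exclusion?**

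Let q be the chance that a dosed patient is later found ineligible. The documents do not give it, so the values here are assumptions. For 10 dosed patients the chance of at least one is 1 − (1 − q)^10: 26% at q = 3%, 40% at 5% and 65% at 10%.

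**The case against.** The strongest reply is that little is lost. The patient stays in Active Monitoring, the events go through section 10 reporting, the stopping rule counts them, and grade 4 and 5 events judged unrelated are reviewed as well. That stands. A reader might infer that the patient vanishes from the trial's safety data, and the documents do not support that: only the 16.42 tables are affected. Section 16.42 also implies the exclusion by saying who is included. It does not spell the exclusion out.

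A reader might also infer that the rates are biased downwards. Some entry criteria are safety screens (organ function in 3.16, autoimmune disease in 3.30, prior pneumonitis in 3.31), so a breach of one could plausibly go with more events. But 13.7 covers every criterion, including the biopsy window, the minimum skin score for stage IB/IIA disease and washout periods. It also makes continued treatment conditional on the absence of safety concerns. No passage says that ineligible patients have more events, and dropping an event-free patient raises the rate.

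It is tempting to say that the tables would disagree with what the DSMB sees. Section 16.61 gives no denominator for the DSMB reports, so this is not established. Calling 16.42 and 16.63 contradictory is also too strong. One is a trigger for suspending accrual and the other a final description. Their bases are inconsistent, but both can be followed, and once the tenth patient is enrolled there is little accrual left to suspend.

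Finally, the safety goal speaks of this patient population, which gives an eligible-only set some basis, and section 6.2 has eligibility verified before registration. Both are fair points. They support an eligible-only table as an addition. They do not justify having no table of all exposed patients.

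**Conclusion.** The point holds for the adverse-event rates and frequency tables in section 16.42. As written, they would omit any dosed patient later found ineligible and would use a different denominator from section 16.63. Each such patient is 10% of the exposed group at the final accrual of 10. In the low-count examples, one exclusion lowers a rate by 8.9 to 10.0 points if that patient had the event and raises it by 1.1 to 2.2 points if not.

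The conclusion assumes that at least one dosed patient is found ineligible. The documents report none and give no rate, and the pooled 10% allowance in 16.31 is a planning figure, neither an estimate nor a ceiling. If no such patient arises, no result changes.

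Severity is moderate. The effect is on a descriptive secondary analysis; the primary endpoint, the decision rules and participant monitoring are untouched.

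**What to change.** In the adverse-event paragraph of section 16.42, define the analysis set as all patients who received at least one dose of pembrolizumab, regardless of eligibility status. State that adverse events are exempt from the eligibility restriction in that section's opening sentence. This agrees with the treated-patient base of section 16.63 and removes any effect of when ineligibility is determined. Leave the efficacy sets as they are. An eligible-only adverse-event table can be kept as supportive.

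The cost is about one sentence. Section 13.7 already keeps these patients under monitoring, so no new data or patients are needed and power does not change. The small downside is that reported rates may shift slightly, in either direction, and will include patients outside the target population.

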4.2 Survival Follow-up

	Survival Follow-up				
	q. 3 months until PD	At PD	After PD q. 3 months	Death	New Primary
Survival Follow-up	X	X	X	X	At each occurrence

1. If a patient is still alive 2.5 year after registration, no further follow-up is required.

5.0 Stratification Factors OR Grouping Factor:

None.

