11.2 Evaluation of Measurable Disease

11.21 Evaluation of primary cutaneous lesion

mSWAT is calculated using body surface area (BSA) of each MF lesion (palm plus fingers of the patient $\approx 1\%$ BSA) in each of 12 areas of the body, multiplying the sum of the BSA of each lesion type by a weighting factor (patch=1, plaque=2, and tumor =4) and generating a sum of the subtotals of each lesion subtype.

11.211 Measurement of effect

- Overall cutaneous response rate (ORR) = proportion of patients with a 50% or greater reduction of baseline mSWAT score
- Complete cutaneous response rate (CR) = proportion of patients with a 100% reduction of baseline mSWAT score
- Cutaneous 90 response rate (CR90) = proportion of patients with a 90% or greater reduction of baseline mSWAT score without the development of new tumors
- Cutaneous partial response rate (PR) = proportion of patients with a 50-90% baseline reduction of mSWAT score without the development of new tumors
- Progressive cutaneous disease (PD) = greater than 25% increase in baseline mSWAT or the development of new tumors. However, if in the judgement of the investigator, the increase in mSWAT is the result of inflammation due to treatment and/or the unmasking of subclinical skin involvement, this increase in mSWAT shall not be considered evidence of progressive cutaneous disease and the patient shall otherwise be classified as stable cutaneous disease (SD).
- Stable cutaneous disease (SD) = <25% increase to <50% reduction in baseline mSWAT without the development of new tumors ; or patients with a greater than 25% increase baseline mSWAT due to

the result of inflammation due to treatment and/or the unmasking of subclinical skin involvement.

- Relapsed cutaneous disease = Any disease recurrence in those with complete response

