Duration of response is defined for all evaluable patients who have achieved a CR, CR90 or PR as the date at which the patient's objective status is first noted to be a CR, CR90 or PR to the earliest date relapse is documented. The distribution of duration of complete response will be estimated using the method of Kaplan-Meier.

Time to response is defined as the time from registration to CR, CR90 or PR. The distribution of survival time will be estimated using the method of Kaplan-Meier (Kaplan and Meier 1958).

Overall survival time is defined as the time from registration to death due to any cause. Patients are censored if they are alive at the time of analysis. The distribution of survival time will be estimated using the method of Kaplan-Meier (Kaplan and Meier 1958). In addition, the overall survival rate at 2 years after registration will be reported.

Additional Analyses: All endpoints may be analysed using patient characteristics to explore possible associations of demographics with the endpoints. Possible characteristics include clinical stage, gender and prior treatments.

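### The plan promises a 5-year progression-free survival rate but requires follow-up only to 2.5 years; the duration-of-response definition also needs clarifying

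*Combined protocol and SAP*

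**What the plan says.** **Progression-free survival.** Section 16.42 defines PFS for all evaluable patients "as the time from registration to relapse or death due to any cause". The censoring sentence uses a different term: "Patients are censored if they have not achieved a progression at the time of analysis". Kaplan-Meier is the method, and "the progression-free survival rate at 5 years after registration will be reported". Overall survival, in the same section, has a 2-year landmark.

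**Follow-up.** Section 4.2 schedules survival contacts "q. 3 months until PD", then at PD and 3-monthly afterwards. Its footnote says: "If a patient is still alive 2.5 year after registration, no further follow-up is required". Patients who leave for alternative therapy have no follow-up (Sections 13.0 and 13.3). For PD in cycle 1, Section 13.2 has the patient exit without follow-up, whereas the table in Section 13.0 sends progression during active treatment to survival follow-up.

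**Duration of response.** Section 16.42 covers all evaluable patients with CR, CR90 or PR. The interval runs from the first "CR, CR90 or PR to the earliest date relapse is documented". Section 11.211 gives the only definition of relapse: "Relapsed cutaneous disease = Any disease recurrence in those with complete response". The paragraph then says: "The distribution of duration of complete response will be estimated using the method of Kaplan-Meier".

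**Size.** Under Amendment 4 accrual stops at 10 patients (Sections 16.1 and 16.31).

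**The concern.** A landmark rate that will be reported should come from data the plan collects. Here the landmark is twice as long as the follow-up required of a living patient. If the longest-followed patient is censored without an event near month 30, the curve stops there and has no value at month 60. A promised secondary result would then be missing, or would depend on unplanned later data collection.

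The duration-of-response paragraph leaves four choices open: what ends a CR90 or PR, how death is treated, when event-free patients are censored, and whether the estimate covers all responders or only complete responders. Making these choices after the data are seen weakens a named secondary goal (Section 2.23).

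**Working it through.** **1. The landmark against follow-up**

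Inputs: landmark 5 years = 60 months (Section 16.42); required follow-up 2.5 years = 30 months (Section 4.2).

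- Gap: 60 − 30 = 30 months.
- The timing in Section 16.32 does not close it. That timing is stated for the primary endpoint: about 3.75 years after opening, or 24 months of treatment for the last patient. Ten patients at 10 per year take 1.0 year to accrue, so the second option gives the first patient at most about 1.0 + 2.0 = 3.0 years.
- The overall survival landmark, 24 months, does lie inside 30 months.

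**2. The chance that no 60-month estimate exists**

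The document gives no PFS median, so a range is assumed. Take exponential PFS with median *m* months, 10 patients, no other censoring before month 30, and no data after it. The curve has a value at month 60 (namely zero) only if all 10 patients have had an event by month 30:

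P(no estimate) = 1 − (1 − S(30))^10, with S(30) = 0.5^(30/*m*)

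| Assumed median (months) | P(all 10 events by month 30) | P(no estimate at month 60) |
|---|---|---|
| 6 | 0.728 | 0.27 |
| 9 | 0.352 | 0.65 |
| 12 | 0.143 | 0.86 |
| 18 | 0.023 | 0.98 |
| 24 | 0.004 | 0.996 |

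The same check without the exponential form: if true PFS at 2.5 years is 10%, 20%, 30% or 50%, all 10 patients have an event by then with probability 0.349, 0.107, 0.028 or 0.001.

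Exits without follow-up leave fewer patients who could be censored event-free at month 30. If 2 of 10 exit early, the 12-month-median case becomes 1 − (1 − 0.5^2.5)^8 = 0.79.

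**3. Does a 2-year landmark fit?**

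It does for patients who stay in follow-up. Survival contacts are 3-monthly to month 30. For a patient treated to the limit, the last dose on a 21-day grid within 24 months falls 34 × 21 = 714 days after the first. The mSWAT 90 days after that dose (Section 13.6) falls at 714 + 90 = 804 days, or 804/30.44 = 26.4 months, before visit windows. It does not fit for patients who exit with no follow-up, so they need a stated rule.

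**4. Duration of response: the texts side by side**

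- Population: CR, CR90 and PR. End event: relapse. Only definition of relapse: recurrence after complete response. On the literal text, a patient whose best response is CR90 or PR has no defined end event.
- PFS and overall survival each count death as an event and state when patients are censored. Duration of response does neither.
- The population named in the definition (all responders) differs from the one named in the Kaplan-Meier sentence (complete responders).
- Adding PD as the end event exposes a difference of scale. Section 11.211 measures cutaneous PD against baseline mSWAT, while relapse after CR is any recurrence. For example, a patient with baseline 40 and CR90 at 4 could return to 40 without new tumors and still not have PD, because the threshold is 40 × 1.25 = 50. A complete responder fails at any recurrence. One pooled curve would mix the two.
- Complete responders go to survival follow-up (Section 13.3), where neither Section 4.2 nor Section 11.41 schedules an mSWAT.

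**The case against.** The footnote in Section 4.2 says that further follow-up is not required; it does not forbid it. The curve might also reach zero before month 30. A reader might infer that a 5-year rate can never be produced. The documents do not support that; they show only that the plan does not secure one.

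On duration of response, a reader might infer that it cannot be computed for CR90 and PR patients. That is too strong. Section 16.42 also uses relapse as the PFS event, where the endpoint's name and the censoring sentence show that progression is meant. Section 13.0 lists progression and relapse under one reason for stopping treatment. Section 11.211 defines relapsed cutaneous disease, which is not quite the bare word in Section 16.42. Section 1.23 says the efficacy endpoints follow published consensus definitions, which may supply an end event. So relapse may be loose wording for progression. Under either reading, the missing death and censoring rules and the complete-response label remain.

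A reader might also see a conflict over follow-up after CR between Section 13.0 (treatment completed per protocol goes to clinical follow-up) and Section 13.3 (CR goes to survival follow-up). That arises only if CR is coded as completed per protocol, which the documents do not say; Sections 13.3 and 13.5 agree with each other. Section 13.2 could likewise be read as a cycle-1 exception to Section 13.0, but neither section says so.

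**Conclusion.** The 5-year PFS landmark is wrong as written: it lies 30 months beyond required follow-up and no later collection is scheduled. Under the assumptions in the working, the chance of having no estimate runs from 0.27 (6-month median) to 0.996 (24-month median). Early exits lower these figures somewhat, to about 0.79 rather than 0.86 for a 12-month median with 2 of 10 exits. Confidence in this part is high.

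The duration-of-response part is an ambiguity, held with moderate confidence. How many of the 10 patients it affects is not known. The mismatch between relapse and progression in the PFS text is minor wording.

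Only secondary endpoints are affected. No direction of bias is claimed, and the primary response count does not change. The point should be fixed, but it does not undermine the trial's main result.

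**What to change.** **PFS**
- Replace the 5-year rate with a 2-year rate, matching overall survival. Any landmark up to 2.5 years would also fit; keeping 5 years would mean doubling required follow-up.
- Define the event as progression (including relapse after CR) or death, and state that PD in cycle 1 counts as an event.
- State that patients who exit with no follow-up (Sections 13.0, 13.2 and 13.3) are censored at their last assessment unless PD or death was recorded.
- Reconcile Sections 13.0 and 13.2 on follow-up after PD in cycle 1.

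**Duration of response**
- Use that name throughout. End it at the first documented PD, relapse after CR, or death.
- Censor event-free patients at the last visit or contact recorded as free of progression or relapse.
- Report CR separately from CR90 and PR, and say why: PD is measured from baseline mSWAT, whereas relapse after CR is any recurrence.
- State that no mSWAT is scheduled in survival follow-up, so relapse dates after CR are less precise.

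**Cost.** Mostly SAP wording. The 5-year figure is lost, and reported durations may be shorter once PD and death end them. The survival follow-up form must record whether the patient is free of progression or relapse at each contact. The documents do not show that form, so one added field may be needed.

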7.0 Protocol Treatment

7.1 Treatment Schedule

Agent	Dose	Route	Day	Cycles
Pembrolizumab	200 mg	IV	Day 1	q3 weeks until disease progression, intolerable toxicity, or CR for a maximum duration of 24 months

Protocol treatment should be administered on Day 1 of each cycle after all procedures/assessments have been completed as detailed on the Test Schedule (Section 4.0). Trial treatment may be administered up to 3 days before or after the scheduled Day 1 of each cycle due to administrative reasons.

All trial treatments will be administered on an outpatient basis.

Pembrolizumab 200 mg will be administered as a 30 minute IV infusion every 3 weeks. Sites should make every effort to target infusion timing to be as close to 30 minutes as possible. However, given the variability of infusion pumps from site to site, a window of -5 minutes and +10 minutes is permitted (i.e., infusion time is 30 minutes: -5 min/+10 min).

The Pharmacy Manual contains specific instructions for the preparation of the pembrolizumab infusion fluid and administration of infusion solution.

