11.4 Measurement at Follow-up Evaluations

11.41 Cutaneous lesions

- mSWAT will be collected at baseline, end of every cycle of treatment and during clinical follow-up at 30 and 90 days.
- mSWAT response will be recorded as per Section 11.211.

11.42 Target visceral lesions and lymph nodes.

- Subsequent PET-CT scans must be obtained after cycle 4 and the end of treatment visit following initial documentation of objective cutaneous response status of either complete response (CR) or partial response (PR).
- In the case of stable disease (SD), follow-up measurements must have met the SD criteria at least once after study entry at a minimum interval of 3 weeks.
- The cytological confirmation of the neoplastic origin of any effusion that appears or worsens during treatment when the measurable tumor has met criteria for response or stable disease is mandatory to differentiate between response or stable disease (an effusion may be a side effect of the treatment) and progressive disease.

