16.0 Statistical Considerations and Methodology

16.1 Overview

This is a phase II study designed to assess the overall cutaneous response rate at cycle 9 in MF patients treated with pembrolizumab. It is a single one-stage design with an interim analysis based on the Simon optimal design with 85% power and 10% Type I error.

NOTE: As per Amendment 4, accrual will cease after the enrollment of 10 patients due to sponsor decision on funding. Thus, the study power and type I error will not be appropriate for the analysis, as the study will not be able to go to full accrual. The study will be analyzed at the pre-defined interim step.

16.11 Endpoint:

The primary endpoint is overall cutaneous response (cutaneous complete response (CR), cutaneous 90 response (CR90) or cutaneous partial response (PR)) as defined using the mSWAT score as stated in section 11.0. Throughout Section 16.0, CR, CR90 or PR will be considered synonymous with “success”, unless specified otherwise. All patients meeting the eligibility criteria who have signed a consent form and have begun treatment will be evaluable for response.

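### Duration of response and time to response both hinge on a single unconfirmed mSWAT visit, so reading error can add responders just short of a 50% reduction and date true responses too early

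*Combined protocol and SAP*

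**What the plan says.** **Endpoints (16.42).** Duration of response runs from the date a patient's "objective status is first noted to be a CR, CR90 or PR" to the earliest documented relapse. For the other endpoint, "Time to response is defined as the time from registration to CR, CR90 or PR".

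**Response criteria (11.211).** Cutaneous PR is the "proportion of patients with a 50-90% baseline reduction of mSWAT score without the development of new tumors". CR90 and CR need falls of at least 90% and of 100%, and CR90 also excludes new tumors. None of the three carries a confirming visit or a minimum duration. The CR90 category exists only in this skin section, so the response labels in 16.42 read most naturally as skin status.

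**Readings.** Section 11.41 states: "mSWAT will be collected at baseline, end of every cycle of treatment and during clinical follow-up at 30 and 90 days". The test schedule sets a cycle at 21 days. Section 7.1 continues treatment "until disease progression, intolerable toxicity, or CR for a maximum duration of 24 months".

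**Design.** Section 16.1 describes a "single one-stage design with an interim analysis based on the Simon optimal design with 85% power and 10% Type I error". There is no comparator, and no blinded or independent mSWAT reading is described. Accrual stops at 10 patients under Amendment 4.

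**Primary endpoint (16.41).** This uses one time point: "The mSWAT score at baseline and cycle 9 will be used for change in baseline calculations".

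**The concern.** mSWAT is built from palm-sized estimates of involved area over 12 body regions, weighted by lesion type, so some variation between readings is to be expected. When the first qualifying visit settles the matter, every further visit gives a patient sitting just short of 50% another chance to cross by error. One crossing makes that patient a responder in both summaries. For a patient who is truly improving through 50%, the same mechanism tends to put the response date too early. The time-to-response curve moves up and to the left, and the duration-of-response set can take in patients without a sustained response.

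Two features of the plan add to this. First, 11.211 lets the investigator set aside a rise above 25% as inflammation or unmasking of subclinical disease, so the plan accepts that mSWAT can move without a true change in disease. It offers no matching check on a fall. Second, duration of response ends at relapse, which 11.211 defines only for complete responders. A PR seen at one visit that drifts back to stable disease has no clearly defined end.

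With 10 patients, each one is 1/10 = 10% of the sample, and 16.34 names quality and duration of response among the matters weighed in decisions about the study.

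**Working it through.** The plan states no figure for reading error, confirmation or number of readings, so there is nothing of its own to reproduce here.

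**1. Number of readings.** 24 months is 24 × 365.25/12 = 730.5 days, and 730.5/21 = 34.8. The maximum is therefore about 35 on-treatment readings, or 37 with the two clinical follow-up visits. Patients who reach CR, progress or stop early have fewer. Nine readings take a patient to the end of cycle 9 (9 × 3 = 27 weeks).

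**2. Model (assumed, not from the documents).** With true reduction d held constant, the observed ratio to baseline at visit j is (1 − d) × exp(e_j − b). Here b is the baseline reading error and e_j the visit error, each normal with mean 0 and SD s on the log scale, independent between visits. A false hit occurs when the ratio is 0.5 or less, that is, when e_j − b ≤ ln(0.5/(1 − d)). For d = 0.30 the limit is ln(0.5/0.7) = −0.336.

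**3. One fixed reading.** P = Φ(−0.336/(s√2)):
- s = 0.10: Φ(−2.38) = 0.9%
- s = 0.15: Φ(−1.59) = 5.6%
- s = 0.25: Φ(−0.95) = 17.1%

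**4. Repeated readings.** Given b, each visit is a hit with probability Φ((−0.336 + b)/s). The chance of at least one hit in K visits is 1 − (1 − that)^K, averaged over b. That chance and the chance of two consecutive hits were obtained by simulation with at least 100,000 patients per cell, true reduction 30%:

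| Log SD | One fixed reading | Any of 9 | Two in a row in 9 | Any of 35 | Two in a row in 35 |
|---|---|---|---|---|---|
| 0.10 | 0.9% | 5% | 0.6% | 13% | 1.6% |
| 0.15 | 5.6% | 26% | 6% | 45% | 13–14% |
| 0.25 | 17.1% | 54% | 23% | 75% | 39–40% |

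**5. Sensitivity over 9 visits.**
- True reduction 20%, SD 0.25: about 36% single, 11% confirmed.
- No true change: 0.4% single at SD 0.15 and 4.6% at SD 0.20.
- Half the error variance a stable reader effect that cancels against baseline, true reduction 30%: 36% single and 11% confirmed at SD 0.25; 7.5% and 0.9% at SD 0.15.
- 80% of the variance stable: 10% and 1% at SD 0.25; 0.2% single at SD 0.15.

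In every row of the table confirmation lowers the false-hit rate, but at the larger errors it does not remove it. The early dating of true responses follows from the same mechanism and was not simulated.

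**The case against.** The strongest reply is that the size is wholly assumed. The documents give no mSWAT reading error, and the 54% needs log SD 0.25, a 30% reduction held from the first visit, and independent errors. A single dermatologist's habits may well persist from visit to visit, which lowers the figures sharply. This stands, and it is why only a range can be given.

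Section 11 also surrounds the score with other evidence: a dermatology examination, standardized photography, supporting documentation of response, and a no-new-tumors condition for PR and CR90. These make a response more than a bare number, but none is a repeat reading. The PET-CT that 11.42 requires is a nodal and visceral check.

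A reader might set the gap against the interval rule in 11.42, "In the case of stable disease (SD), follow-up measurements must have met the SD criteria at least once after study entry", with its 3-week minimum, and call it an internal contradiction. It is not one: that rule sits under target visceral lesions and lymph nodes, so its absence from the skin criteria contradicts nothing.

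Section 1.23 says the endpoints conform to cited consensus definitions. Whether that source requires confirmation cannot be checked from the documents; the protocol's own definitions do not. If comparability with published work is the worry, reporting both versions meets it.

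Finally, a plain two-visit rule could do harm. Under 13.3 and 13.5 a patient who reaches CR goes to survival follow-up, and the schedule in 4.2 lists no mSWAT. Someone moving straight from stable disease to CR could then never be confirmed. This stands, and the fix has to provide for it.

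**Conclusion.** The point holds as a cheap improvement to two descriptive secondary endpoints. One unconfirmed visit decides who enters duration of response and when time to response ends. Under the assumptions shown (log SD 0.10 to 0.25, independent errors, constant true reduction of 30%), the chance of a false responder over 9 visits is about 5% to 54%, and 0.6% to 23% with two consecutive visits. The exposure is mainly among partial improvers.

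Three stronger readings are tempting and not supported:
- That measurement noise does create responders here, or that it fills the duration-of-response set. The documents hold no reading error from which to conclude that; they show only that it can happen.
- That every patient has 35 chances. That number is a ceiling for patients who stay on treatment for 24 months.
- That the primary result is inflated in the same way. The primary analysis takes one reading at cycle 9, or the last observation carried forward. That reading is also unconfirmed, but it is not the best of many.

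**What to change.** In 16.42, for duration of response and time to response only:
- Define the response date as the first of two consecutive scheduled mSWAT assessments that both meet CR, CR90 or PR (at least a 50% reduction, no new tumors).
- Count a CR immediately preceded by CR90 or PR as confirmed.
- Where the first response is a CR and no later mSWAT is scheduled because the patient has gone to survival follow-up, keep it in the analysis, flagged as unconfirmed.
- Report the first-noted version alongside as a sensitivity analysis.

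Leave the cycle-9 primary endpoint and the treatment rules unchanged.

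The cost is a few lines of analysis text, using readings already scheduled. The downside is slightly fewer responders in these two summaries, and a first PR or CR90 at a patient's last mSWAT cannot be confirmed; the sensitivity analysis shows how much that matters.
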